#### 3.5.2 Baseline and randomization

- Screened subjects complete a baseline program that includes: weight, physical examination, vital
- signs, hematology, urinalysis, blood biochemistry, thyroid function, 12-lead electrocardiogram,
- 706 respiratory function (%FVC), grip strength, ALSFRS-R scale, ALSAQ-40 scale, and
- cerebrospinal fluid collection (if consented). Women of child-bearing potential undergo a urine
- 708 pregnancy test. Repeat testing is not required if the same items are checked at baseline and
- screening and the results within 7 days.
- 710 Once inclusion and exclusion criteria have been verified, randomization number will be
- 711 requested for distribution of the drug, and subjects will be instructed on how to take the
- 712 medication at the study center. The first dose of medication will be taken on the day after
- randomization (Day 1). Diary cards will be distributed and subjects will be instructed to record
- 714 concomitant medication and AEs.

3.5.3 Clinic Visit

715

# **3.5.3.1 Time of Clinic Visit**

- Subjects will be followed up at the study center at day  $30 \pm 3$  (V2), day  $90 \pm 7$  (V4), and day 180
- 718  $\pm$  7 (V7) after randomization. During the course of the trial, the investigator may increase the
- visit depending on the patient's condition, and record in the medical record form.

#### **3.5.3.2 Items of Clinic Visit**

- Each clinic visit should evaluate and record the occurrence of AEs, concomitant medication,
- dispense IMP and return the unused IMP, and dispense and return of diary cards.
- 723 V2, V4: weight, ALSFRS-R score, grip strength, respiratory function (%FVC), vital signs,
- 724 physical examination, electrocardiogram, hematology, urinalysis, blood biochemistry, urine
- 725 pregnancy, and thyroid function will be test.
- 726 V7: Weight, physical examination, vital signs, hematology, urinalysis, blood biochemistry,
- 727 thyroid function, 12-lead electrocardiogram, respiratory function (%FVC), grip strength,
- 728 ALSFRS-R scale, ALSAQ-40 scale, centralized blood collection (if consent), cerebrospinal fluid
- 729 collection (if consent), and urine pregnancy in women of childbearing age.

# **3.5.4 Phone Visit**

# **3.5.4.1 Time of phone Visit**

- After signing the informed consent form, subjects will be visited by phone at the Screening
- Period, Day 7 (V1), Day  $60 \pm 3$  (V3), Day  $120 \pm 3$  (V5), Day  $150 \pm 3$  (V6), and the 2nd weeks
- after the end of the trial.

# **3.5.4.2 Items of phone Visit**

- 736 The visits (V1, V3, V5 and V6) will be to inquire and teach about treatment compliance in
- 737 addition to documenting AEs and concomitant treatments (medication & non-medication). On
- days  $60 \pm 3$  (V3),  $120 \pm 3$  (V5), and  $150 \pm 3$  (V6), subjects will be encouraged to follow up in
- the hospital, where vital signs, physical examination, and weight will be recorded. If the subject
- unable to the hospital, family will be required to the hospital at the scheduled visit to collect new

medication and diary cards. The post-study visit will take within 2 weeks of the end of the trial.

# 742 **3.5.4.3 Post-study Visit**

- Subjects will be followed up by phone within the 2nd week after the last dosing, and will be
- asked if they are experiencing any discomfort such as dizziness, headache, vomiting, etc. The
- 745 eCRF for the phone visit will complete.

#### 746 3.5.5 Visit for Subjects Who Withdraw Early"

- 747 If subject is randomized and treated with the IMP and withdraws early for reasons attributable to
- 748 the subject or at the discretion of the investigator, the subject should come to the study site to
- 749 complete the withdrawal visit: weight, physical examination, vital signs, hematology, urinalysis,
- blood biochemistry, thyroid function, 12-lead electrocardiogram, respiratory function (%FVC),
- 751 grip strength, ALSFRS-R scale, ALSAQ-40 scale, urine pregnancy test in women of childbearing
- age. Documentation of concomitant treatments (medication & non-medication), monitoring and
- recording of AEs and SAEs up to 14 days after the last dosing.

# 754 **3.6 Visit Description**

# 755 **3.6.1 Screening Visit**

- The following twice procedures will be performed at a clinic visit to determine the subject's
- 757 eligibility for the study.

#### 758 First screening

- 759 (1) Signing informed consent;
- 760 (2) Obtaining a detailed medical history, allergy history, medication history, smoking history,
- alcohol history, and assessment of demographic information;
- 762 (3) Height and weight;
- 763 (4) Routine physical examination and vital signs;
- 764 (5) Laboratory tests: hematology, urinalysis, blood biochemistry, 12-lead electrocardiogram,
- and urinary pregnancy test for women of childbearing potential;

- Protocol No.: MP-2019-004
- 766 (6) Respiratory function test (% FVC);
- 767 (7) Grip strength test;
- 768 (8) ALSFRS-R scale;
- 769 (9) MMSE scale;
- 770 (10) Verification of inclusion and exclusion criteria;
- 771 (11) Reminding subjects to visit the center for next time for screening tests.
- 772 **Second Screening** (90  $\pm$  3 days apart from the first)
- 773 (1) ALSFRS-R scale;
- 774 (2) Recording of concomitant medications;
- 775 (3) Monitoring and recording of AEs and SAEs.
- NOTE: Twice ALSFRS-R scores are performed to confirm that the subject meets the inclusion
- criteria, and should be performed 90  $\pm$  3 days apart between the twice. If the subject has
- ALSFRS-R score examination within 3 months prior to this trial, the results may be used as the
- 779 first ALSFRS-R score during the Screening Period, upon presentation of appropriate
- 780 documentation (e.g., medical records).
- 781 **3.6.2 Baseline Period**
- 782 (1) Routine physical examination, vital signs, weight;
- 783 (2) Laboratory tests: hematology, urinalysis, blood biochemistry, thyroid function, 12-lead
- electrocardiogram, urine pregnancy test for women of childbearing age;
- 785 (3) Respiratory function (%FVC);
- 786 (4) Grip strength test;
- 787 (5) ALSFRS-R scale;
- 788 (6) ALSAQ-40 scale;

- 789 (7) Verification of inclusion and exclusion criteria;
- 790 (8) Cerebrospinal fluid collection (if agreed, then sent to the central laboratory);
- 791 (9) Recording of concomitant medications;
- 792 (10) Monitoring and recording of AEs and SAEs.
- Note: After passing the screening, subject can enter the baseline period. If the same items are
- examined during the baseline and screening periods and the results within 7 days, repeat testing
- 795 is not required.
- 796 **3.6.3 Randomization (Day 0)**
- 797 (1) Assign randomization numbers in a randomized system;
- 798 (2) Dispense IMP and confirm that is enough for use until the next visit;
- 799 (3) Instruct subjects in the use of the IMP and have subjects use the study drug as prescribed by
- the investigator;
- 801 (4) Instruct females of childbearing potential to use contraception throughout the course of the
- study;
- 803 (5) Distribute and instruct in the use of the subject diary;
- 804 (6) Record the concomitant medications;
- 805 (7) Remind subjects that a phone visit on Day 7 of dosing.
- Note: The first dosing of IMP started the day after randomization is (Day 1).
- 807 **3.6.4** Visit 1 (Day 7, phone visit)
- 808 (1) Inquire and record the occurrence of AEs and concomitant medication;
- 809 (2) Inquire treatment compliance;
- 810 (3) Remind the subject or his/her family to collect the next month's drug and diary card from the
- study center and return the unused medication and diary card at the same time.

- 812 3.6.5 Visit 2 (Day  $30 \pm 3$ )
- 813 (1) Routine physical examination, vital signs, weight;
- 814 (2) Respiratory function (%FVC);
- 815 (3) Grip strength test;
- 816 (4) ALSFRS-R scale;
- 817 (5) Laboratory tests: hematology, urinalysis, blood biochemistry, thyroid function, urine
- pregnancy test for women of childbearing age;
- 819 (6) 12-lead electrocardiogram;
- 820 (7) Verify and return all unused IMP and used and unused packages;
- 821 (8) Record the AEs and concomitant medications;
- 822 (9) Verify, return and distribute diary cards to subjects;
- 823 (10) Dispense IMP and confirm that the drug will be enough until the next visit;
- 824 (11) Make an appointment with the subject for the next visit.
- 825 3.6.6 Visit 3 (Day  $60 \pm 3$ , phone visit)
- 826 (1) Weight;
- 827 (2) Physical examination;
- 828 (3) Vital signs;
- 829 (4) Inquire and record AEs, concomitant medications;
- 830 (5) Inquire treatment compliance;
- 831 (6) Remind the subject or his/her family members to come to the center to get the next month's
- medications and diary card and return any unused medication and diary card at the same time.
- 833 3.6.7 Visit 4 (Day  $90 \pm 7$ )
- 834 (1) Routine physical examination, vital signs, weight;

- Protocol No.: MP-2019-004
- 835 (2) Respiratory function (%FVC);
- 836 (3) Grip strength test;
- 837 (4) ALSFRS-R scale;
- 838 (5) Laboratory tests: hematology, urinalysis, blood biochemistry, thyroid function, urine
- pregnancy test for women of childbearing age;
- 840 (6) 12-lead electrocardiogram;
- 841 (7) Verify and return all used IMP and used and unused packages;
- 842 (8) Record the AEs and concomitant medications;
- 843 (9) Verify, return and distribute diary cards to subjects;
- 844 (10) Dispense IMP and confirm that the drug will be enough until the next visit;
- 845 (11) Make an appointment with the subject for the next visit.
- 847 3.6.8 Visit 5 (Day 120  $\pm$  3)
- 848 (1) Weight;

- 849 (2) Physical examination;
- 850 (3) Vital signs;
- 851 (4) Inquire and record AEs, concomitant medications;
- 852 (5) Inquire treatment compliance;
- 853 (6) Remind the subject or his/her family members to come to the center to get the next month's
- medication and diary card and return any unused medication and diary card at the same time.
- 855 3.6.9 Visit 6 (Day 150  $\pm$  3)
- 856 (1) Weight;
- 857 (2) Physical examination;

Version 1.1 / Jul 29, 2020 *confidential* Page 42 of 91

- Protocol No.: MP-2019-004
- 858 (3) Vital signs;
- 859 (4) Inquire and record AEs, concomitant medications;
- 860 (5) Inquire treatment compliance;
- 861 (6) Remind the subject or his/her family members to come to the center to get the next month's
- medication and diary card and return any unused medication and diary card at the same time.
- 863 **3.6.10 Visit 7 (Day 180 \pm 7)**
- 864 (1) Routine physical examination, vital signs, weight;
- 865 (2) Laboratory tests: hematology, urinalysis, blood biochemistry, thyroid function, urine pregnancy test for women of childbearing age;
- 867 (3) 12-lead electrocardiogram;
- 868 (4) Respiratory function (%FVC);
- 869 (5) Grip strength test;
- 870 (6) ALSFRS-R scale;
- 871 (7) ALSAQ-40 scale;
- 872 (8) Cerebrospinal fluid collection (if agreed, then sent to the central laboratory)
- 873 (9) Blood Collection for Drug Concentration Studies (sent to the central laboratory)
- 874 (10) Verify and return all used IMP and used and unused packages;
- 875 (11) Verify and return diary cards;
- 876 (12) Record the AEs and concomitant medications.
- 877 3.6.11 Safety follow-up after discharge / withdrawal
- Follow-up phone call within 2 weeks of discharged / withdrawal to inquire about symptoms such
- as dizziness, headache, and vomiting, and complete an eCRF for the visit.
- 880 3.7 Plasma and cerebrospinal fluid drug concentration studies, Measurement of

# Biomarker Levels in Cerebrospinal Fluid

- 882 Collection of plasma and cerebrospinal fluid from subjects, and determinate of TBN and its
- metabolite 5-OH-TBN in plasma and cerebrospinal fluid and biomarker in cerebrospinal fluid.
- 884 Collection of plasma and cerebrospinal fluid requires the following steps:

# 885 Screening Period

- 886 Signed informed consent for collection of blood and cerebrospinal fluid for drug concentration
- studies.

881

- 888 Baseline period and Visit 7 (Day 180  $\pm$  7)
- Subjects who sign the informed consent form will have their cerebrospinal fluid collected at any
- time of baseline period. Blood sample for the drug concentration study will be collected prior to
- 891 the first dose of medication on the day of Visit 7 (Day 180  $\pm$  7), and then a blood and
- 892 cerebrospinal fluid sample will be collected 3±0.5 hours after the first dosing of drug on the
- same day (based on the  $T_{max}$  time for the PK of the TBN Tablets Phase I clinical trial). 4 mL of
- 894 blood samples and 4 mL of cerebrospinal fluid will be collected each time. The collection,
- 895 dispensation, preservation, transportation, and test are in strict accordance with the Central
- 896 Laboratory Service Manual. No more than 10 subjects per group shall be tested for blood
- samples and cerebrospinal fluid for drug concentration study. Cerebrospinal fluid biomarker
- testing will be performed on all subjects who consent as possible.

# 894 THE MANAGEMENT OF IMP

#### 4.1 Investigational medicinal product (IMP)

#### 901 **4.1.1 Treatment Groups**

900

- 902 (1) TBN tablets: strengths: 100 mg/tablet and 300 mg/tablet, provided by Guangzhou Magpie
- 903 Pharmaceuticals Co., Ltd.
- 904 (2) Placebo: Excipient tablets without TBN, strengths: 100 mg/tablet and 300 mg/tablet,
- 905 provided by Guangzhou Magpie Pharmaceuticals Co., Ltd.

412	Mode	of Ad	minici	tration
4.1.4	vioue	OI AU		Hallon

- Treatment Group 1: TBN tablets 600 mg group (TBN 300 mg × 2 tablets + placebo 300 mg × 2
- tablets are taken orally twice daily, TBN 100 mg  $\times$  6 tablets + placebo 100 mg  $\times$  6 tablets instead
- if the subjects are not able to take 300 mg tablets because of disease progression).
- 910 **Treatment Group 2:** TBN tablets 1200 mg group (TBN 300 mg× 4 tablets are taken orally
- twice daily, TBN 100 mg  $\times$  12 tablets instead if the subjects are not able to take 300 mg tablets
- 912 because of disease progression).
- 913 **Control Group:** placebo group (placebo 300 mg × 4 tablets are taken orally twice daily, placebo
- $100 \text{ mg} \times 12 \text{ tablets instead if the subjects are not able to take } 300 \text{ mg tablets because of disease}$
- 915 progression).

- **Dosage and Administration:** orally administered, twice a day, once in the morning and evening
- 917 (or the interval  $\geq 8$  hours), at least 1 hour before meals ( $\geq 1$  hour before meals) or at least 2 hours
- after meals ( $\geq 2$  hours after meals), for  $180 \pm 3$  days.
- Note: If the subjects are not able to take 300 mg tablets of TBN or placebo because of disease
- progression, the tables may be exchanged for the 100 mg/tablet, with no change in the dose.
- During the treatment, subjects should record the time and dose of the drug in the subject's diary
- 922 card. Any adverse reactions should be promptly treated and recorded in the original medical
- 923 records.

# 924 **4.2** Preparation/Package/Storage/Responsibility

# 925 4.2.1 Packaging and Labeling of IMP

- 926 Packaging specification: the packaging material is 60 ml oral solid medical high-density
- 927 polyethylene (HDPE) bottle with child protection cover, containing silica gel desiccant and
- 928 deoxidizer, 25 pills/bottle.
- The labels of 100 mg TBN tablets/placebo and 300 mg TBN tablets/placebo are as follows:

# Investigational Product for Clinical Studies of TBN tablet (Phase II, Protocol No.: MP-2019-004)

Clinical Study Approval Letter No: CXHL2000168 / CXHL2000169

Drug No:

Protocol No.: MP-2019-004

Indication: Amyotrophic lateral sclerosis (ALS)

Dosage and Administration: oral (see the protocol for specific dosing regimen)

Dosage Form: Tablet

Strength: 100 mg/tablet or 300 mg/tablet

Storage: Away from light, sealed, and under room temperature (15 °C-30 °C)

Batch No: See the product label for details.

Expiry Date: See the product label for details.

Sponsor: Guangzhou Magpie Pharmaceuticals Co., Ltd.

Note: For clinical study only. Consult your doctor if you have any questions.

# **4.2.2** Dispensing of IMP Numbers

930

932

933

934

935

937

938

939

940

941

In this study, the central random system will be used to generate a random unique number for

subjects having passed the screening and match a corresponding code of IMP. The drug is then

administered according to the randomization. The use and return of each bottle of drug should be

documented on a specified record sheet.

#### 4.2.3 Storage and Dispensing of IMP

The dispensing and management of IMP should be carried out in accordance with the protocol.

According to the registration regulations, only the subjects who enrolled the study are able to

obtain the IMP; only the delegated person at each study site could dispense and store the IMP.

No IMP should be provided to any third parties or any person other than the clinical study

participants. The IMP should be stored properly and only limited number of staffs have the

access to where IMP are stored. The monitor is responsible to ensure that the amount of IMP is

consistent with the amount on the IMP dispensing records.

The IMP should be away from light, sealed and stored under room temperature (15 to 30 °C).

- The study site should designate a dedicated person to be responsible for the storage and
- dispensing of IMP and document on a specified sheet.
- 946 **Notice**
- Drugs should be kept in their original packaging;
- Check the packaging before first use. If the package seal is damaged or the drug is lost, it
- should not be used;
- Save all remaining IMP and packaging.
- **4.2.4 Inventory of IMP**
- 952 It is the responsibility of the investigator to ensure that the quantity of IMP is in line with the
- documented quantity, and to save the record of the drug registration. As required by regulations,
- 954 the investigator or delegated person must maintain the records of the use and return of IMP
- 955 throughout the study, including the amount of the IMP receipted, the amount of the IMP stored
- and/or dispensing, and the amount of the IMP returned to the study site.
- When the IMP is delivered to each study site, the investigator or the delegated person must sign
- 958 the drug receipt form. The list includes: the package number, quantity of IMP and the date of
- 959 receipt. The investigator or the delegated person should record all IMP on a specified record
- 960 form. At the end of the study, the amount of IMP on the sheets should be consistent with the
- amount of drugs stored in the center, the amount of drugs delivered to the subjects, and the
- amount of drugs that the subjects later returned, and there should be a reasonable explanation for
- any discrepancies. All containers and unused IMP should be returned and signed on the return
- 964 form. In most cases, the returned drugs are collected centrally in Guangzhou Magpie
- 965 Pharmaceuticals Co., Ltd. for subsequent destruction; in rare cases, the returned IMP are
- destructed at each research center. Destruction of the drug is carried out by delegated person. The
- process of destruction will be documented and archived.

#### 4.2.5 Transportation of IMP

968

- All IMP used in the trial are provided by Guangzhou Magpie Pharmaceuticals Co., Ltd. and are
- 970 transported by the courier company delegated by Guangzhou Magpie Pharmaceuticals Co., Ltd.

- During the transportation, the temperature should be kept within a specified temperature range,
- and a thermometer with real-time temperature monitoring should be used to monitor the drug
- 973 transportation. After receiving the drug, the drug clinical trial institution should present the
- 974 receipt certificate and accurately record all the IMP received and the date of receipt.

# 5 METHODS FOR REDUCING BIAS: RANDOMIZATION AND BLINDING

#### 5.1 Randomization

975

976

- 977 This study uses Interactive Web Response System (IWRS) to dispense random numbers and
- 978 corresponding IMP. Subjects' random numbers are generated by independent statisticians
- 979 unrelated to the study using SAS 9.4 software or higher version. The subject-drug randomization
- table is in duplicate, sealed and handed over to the main study unit and the sponsor.
- After a 90 day observation period, eligible subjects are to be randomly assigned to high or low
- dose of the IMP group or placebo group (1:1:1). The investigator log into the IWRS system,
- 983 where they are to be given a random number and a drug code.
- In order to ensure that the number of patients in each trial group is similar and the distribution of
- 985 important prognostic factors is balanced, this study uses the minimization method in dynamic
- 986 randomization. The stratification factors are: the diagnostic grade of ALS (clinical diagnosis vs
- 987 clinical diagnosis and laboratory support The diagnostic criteria for clinical diagnosis), the
- 988 change in ALSFRS-R scores during observation period (-1 or -2 vs -3 or -4) and age (<65 years
- 989 vs >65 years).
- 990 Once having been randomly assigned in the study, subjects withdrawing from the clinical trials
- 991 for any reason, regardless of whether or not having been administered with the IMP, will retain
- their random number and the subject will not be allowed to subjects in the trial again.

#### 5.2 Blinding

993

- The study is designed as a double-blind, which means that participants, investigators, supervisors
- and data analyzers are unaware of the assignment of subjects. The statistical analysts randomly
- assign subjects to the treatment or control groups, and keep the distribution information in the
- 1997 IWRS system. The sponsor or its delegated unit shall, in accordance with the relevant provisions

- of the GCP on the administration of IMP, uniformly pack and label the IMP and label them for clinical trials, and pack them by relevant personnel. Each drug shall be packaged in a separate package. The whole process should be checked and recorded in detail by delegated person. After the IMP are transported to study sites, the study sites shall set up a special place (drug depository)
- 1002 for safekeeping by delegated person.
- The blinding of drug is conducted by statisticians and staffs from sponsor who are irrelevant with the study. The TBN and placebo are labeled based on the randomization table. The process of
- blinding should be documented and signed by relevant person.

# 5.2.1 Emergency Unblinding

1006

1007

1008

1009

1010

1011

1012

1013

1014

1015

Investigators cannot open the unblinding envelope unless there is a medical reason for it. On occurrence of a SAE or emergency rescue required by the subject, the responsible investigator of the site should notify the principal investigator to decide whether to open the emergency unblinding envelope for identification of the drug administered before providing prompt rescue or taking appropriate measures. Once the emergency unblinding envelope is opened, the subject will be considered a drop-out. Meanwhile, the investigator should record the information relevant to the unblinding in detail, including the unblinding time, the reason, the study treatment, and the outcome of the rescue. The principal investigator should notify the sponsor in written format as soon as possible and describe the details and necessity of the unblinding.

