# **6.2.4** Management of SAEs

1214 Any SAE must be treated immediately with appropriate therapeutic measures.

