# 1322 **7.2 Subject Withdrawal**

# 1323 7.2.1 Withdrawal Determined by Investigator

- The investigator decides to withdraw subjects from the study, including following situations:
- 1325 (1) There are some complications or special physiological changes in the subjects during the study, which are not suitable for further study;
- 1327 (2) Poor compliance of subjects, which affect safety and efficacy evaluation;
- 1328 (3) Subjects who have SAEs and are not suitable to continue the study;
- 1329 (4) Other circumstances that the investigator determines require withdrawal from the study.
- 1330 The proposed indication of TBN is ALS, which is a progressive disease with the possibility of
- disability and death. The withdrawal criteria for ALS patients with significant deterioration of the
- 1332 condition are set, and the rescue treatment measures are improved as follows:

- Protocol No.: MP-2019-004
- 1333 1) The patient cannot swallow or come to the hospital for visits, affecting administration and
- routine follow-up, the investigator decides whether the subject withdraws from the trial, and
- follows up regularly until the end of the study.
- 1336 2) The patient has respiratory failure and relies on a ventilator to maintain ventilation (≥ 22 h
- per day for  $\ge 10$  days), which may endanger their life, continuing the trial may affect the
- patients' life safety, and the investigator decides whether the subject withdraws from the
- 1339 trial.

- 1340 3) To protect the subjects, when they have respiratory failure or other emergency situations, the
- department should have the ability to deploy emergency treatment personnel and equipment,
- and use ventilators and other rescue equipment in time, and open the green treatment
- 1343 channel of the department when needed.
- 1344 4) The patient has a serious adverse event or the condition worsens to the point of endangering
- their life. To protect the subject and respect their wishes, the investigator can consider letting
- them withdraw and receive more treatment after assessing their survival status, and follow
- up until the end of the study.

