# 1368 **8.1 Sample Size Estimation**

- The trial is an exploratory study of safety and efficacy, no statistical assumptions will be made
- and no sample calculations.
- This study is expected to enroll a total of 150 subjects, with 50 in each group.

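### Section 5.2.1, as written, puts notifying the principal investigator and the envelope decision before rescue, in conflict with the immediate-treatment rule of section 6.2.4

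*Protocol*

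**What the plan says.** Protocol section 5.2.1 (Emergency Unblinding) first restricts opening the envelope to cases with a medical reason. It then sets the procedure for any SAE and for any subject who needs emergency rescue: the site's responsible investigator "should notify the principal investigator to decide whether to open the emergency unblinding envelope for identification of the drug administered before providing prompt rescue". The sentence goes on to cover other measures besides rescue.

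Section 6.2.4 (Management of SAEs) is a single sentence: "Any SAE must be treated immediately with appropriate therapeutic measures".

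Section 7.2.1, item 3, in the part on patients whose ALS deteriorates, covers respiratory failure and other emergencies. It asks that the department be able to bring in emergency staff and equipment and "use ventilators and other rescue equipment in time".

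**The concern.** An emergency code-break procedure should make plain that care does not depend on the code-break. In 5.2.1 the only timing word, before, sits between the unblinding steps and the rescue, and no sentence says that rescue proceeds regardless. A site that follows the sentence literally would contact the principal investigator and obtain a decision on the envelope first, and treat second.

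The events concerned are the ones where time matters. The SAE definition in section 6.2.1 includes life-threatening events, and the trigger in 5.2.1 also names patients who already need rescue. The decision belongs to a role that 5.2.1 distinguishes from the responsible investigator at the site, and the section gives no fallback if that person cannot be reached. What is at stake is the safety of a patient in an emergency. No estimate, test or analysis set is involved.

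**Working it through.** No arithmetic applies. The check compares three places in the protocol on what sets the rule off, what it requires and in which order.

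| Section | Applies to | Requirement | Step before treatment |
|---|---|---|---|
| 5.2.1 | Any SAE, or a need for emergency rescue | Notify the principal investigator, who decides on the envelope; then rescue or other measures | Yes, as written |
| 6.2.4 | Any SAE | Treat immediately | None |
| 7.2.1, item 3 | Respiratory failure or other emergencies | Departmental capacity; rescue equipment used in time | None |

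**Step 1: do the rules cover the same events?** The trigger in 5.2.1 includes every SAE, so every event governed by 6.2.4 is also governed by 5.2.1. Neither section refers to the other or says which takes precedence.

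**Step 2: what does before attach to?** There are two readings.

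- *Reading A.* It attaches to the notification and the decision. Both then precede rescue.
- *Reading B.* It attaches only to identifying the drug. Identification is then optional, since the envelope may stay closed. But the question put to the principal investigator is whether to identify the drug ahead of rescue, and that can only be answered ahead of rescue. The notification that prompts it comes earlier still.

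On both readings a step of the code-break process precedes treatment. The readings differ only in whether the identity of the drug must also be known.

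**Step 3: is this compatible with 6.2.4?** A rule to treat immediately, without condition, leaves no room for a prior contact and decision. On the written order the two sections conflict.

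**Step 4: what does 7.2.1 add?** Less. Item 3 describes mainly what the department must be able to do, and asks for rescue in time, not immediately. Rescue after a short call could still be in time. It shows the intended direction of care but is not a second direct contradiction.

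**Step 5: can the size be measured?** No. The protocol gives no expected number of SAEs and no time for the notification step. Section 8.1 makes no statistical assumptions at all ("The trial is an exploratory study of safety and efficacy, no statistical assumptions will be made"), so no event rate can be taken from there either.

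**The case against.** The strongest reply is that 5.2.1 governs the envelope and not treatment. Its heading is about unblinding, its first sentence restricts opening the code, and the thing to be decided is whether to open it. The phrase about rescue can be taken as the reason for opening: the drug is identified so that rescue can be suited to it. The sentence itself calls the rescue prompt, which points away from a wait, and the wording may simply be an awkward translation.

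Treatment timing is also set elsewhere, and in stronger terms: 6.2.4 says must, where 5.2.1 says should. Section 4.1.2 asks for prompt treatment of adverse reactions, section 3.4.4 leaves treatment of grade 2 or higher events to the investigator's judgement, and section 1.3.3 lets the investigator use other medicines to control side effects. Section 10.2 refers to a principal investigator in each site, so notification may be a brief local step.

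Most of this stands. It settles the probable intent and keeps the weight low. It does not remove the conflict: the order remains in the operative sentence on either reading, the overlap with 6.2.4 is complete for SAEs, and 5.2.1 contains no statement that care goes ahead. The difference between must and should helps a reader who compares the two sections, but a site in an emergency may consult only one of them.

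A reader might infer that the protocol requires rescue to be withheld until the principal investigator gives permission. The text does not support that. No section tells a site to withhold treatment, and the only act made subject to the principal investigator's decision is opening the envelope.

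**Conclusion.** The point holds as a low-severity conflict of wording in a safety procedure. As written, 5.2.1 places notification and the envelope decision before rescue for any SAE or emergency, while 6.2.4 requires immediate treatment of any SAE. The direct conflict is with 6.2.4 alone; item 3 of 7.2.1 is supporting context.

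The conclusion rests on reading the sentence in 5.2.1 in its stated order. It does not assume that any site would act that way.

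Two stronger readings are tempting and should not be drawn. The first is that patients will be treated late: no delay is shown or can be derived. The second is that all 150 planned subjects are exposed: the sentence operates only when an SAE or emergency rescue occurs, so the enrolment figure says nothing about how many would be affected.

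**What to change.** Replace the ordering sentence in 5.2.1 with wording such as: *Emergency treatment starts at once and does not wait for notification or unblinding; the principal investigator is notified in parallel and decides whether the envelope needs to be opened for a medical reason.*

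This keeps the existing medical-reason condition and the principal investigator's role in the decision, and brings 5.2.1 into line with 6.2.4. Sections 6.2.4 and 7.2.1 need no change. The cost is one sentence in one section, with no effect on design, sample size or analysis.
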